OBJECTIVES The aim of this trial is to explore whether finite treatment with nucleos(t)ide analogues is feasible in patients with HBeAg (Hepatitis B 'e' antigen) negative chronic HBV (Hepatitis B Virus) infection. This aim encompasses an exploration of therapeutic strategies to achieve HBsAg (Hepatitis B surface antigen) loss; specifically the trial is designed to evaluate whether a short course of pegylated interferon after nucleos(t)ide analogue withdrawal stimulates antiviral immunity sufficiently to increase the rate of HBsAg loss.

Loss of HBsAg, the most important serological marker of HBV infection, is widely accepted (including by the Food and Drug Administration (FDA) & European Medicines Agency (EMA)) as an indication of cure in chronic HBV infection and is associated with absence of long term sequelae in non-cirrhotic patients. HBsAg is a cheap and universally available serum marker. Loss of HBsAg allows patients to be discharged from follow-up with consequent health-economic benefits.

DESIGN NUC-B will be a multicentre, randomised, open label trial comparing two management strategies to promote HBsAg loss in patients with HBeAg negative chronic HBV infection.

SAMPLE SIZE A trial with 90% power to detect a difference in HBsAg loss between these groups at the P < 0.05 threshold would require 109 subjects in each arm. Allowing for ~10% withdrawal / dropout in each arm we will aim to recruit 120 subjects to each arm; 240 patients in total.

ELIGIBILITY CRITERIA Adult patients aged 18 and above with chronic HBeAg negative hepatitis B virus infection on nucleos(t)ide analogues treatment for 3 years or more.

TREATMENT/MAIN STUDY PROCEDURES

Registered patients will be followed for 4 – 12 weeks between initial screening and randomisation in order to collect data on quantitative HBsAg levels and anti-viral immune responses. During this period a sub-set of consenting patients will receive a liver biopsy for analysis of fibrosis and necroinflammatory scores, measurement of cccDNA and analysis of T cell and NK cell infiltrates.

If the patient remains eligible, electronic randomisation will then allocate subjects to two arms:

1. Control arm

Patients randomised to the Treatment Withdrawal arm will discontinue their nucleos(t)ide analogue treatment at baseline.

2. Interferon arm

Patients randomised to switch from nucleoside analogues to Pegylated interferon will discontinue their current therapy at baseline. No treatment will be given for 4 weeks and then they will commence pegylated interferon 180 mcg s.c. o.w. α 2a and will continue taking weekly interferon for a total of 16 weeks. They will subsequently discontinue all antiviral medications.

PRIMARY ENDPOINT

HBsAg loss 3 years after randomisation

SECONDARY ENDPOINTS

NI	IC.	-R

Secondary endpoints will look at 1) Efficacy endpoints and 2) Safety endpoints. Efficacy endpoints will look at levels of HBsAg, HBV DNA, antiviral T cells response and changes in NK cells response at various timepoints after randomisation. Safety endpoints will look at proportions of patients with exaggerated hepatitis flare, those resuming nucleos(t)ide analogue therapy and adherence to pegylated interferon therapy.

1 INTRODUCTION

Over 250 million people worldwide (an estimated 300,000 in the UK) are chronically infected with hepatitis B virus (HBV) leading to a million deaths per year from hepatocellular carcinoma or complications of cirrhosis (1). Four phases of disease are recognised in patients with chronic HBV infection; these are defined according to the presence or absence of the hepatitis B 'e' antigen (HBeAg), ALT values and the level of HBV DNA in serum (2). Elimination of infection, which requires clearance of the HBV minichromosome (cccDNA) from hepatocytes, indicated by loss of the HBV surface antigen (HBsAg) is the ultimate goal of management but this is rarely achieved. Treatment is required to arrest progression of disease during the HBeAg +ve hepatitis phase and during the HBeAg -ve hepatitis phase. Over 80% of patients requiring treatment in European countries (including the UK) are in the HBeAg -ve hepatitis phase (3). Treatment options for HBeAg -ve hepatitis are either 12 months of pegylated interferon or indefinite therapy with nucleos(t)ide analogues such as Entecavir or Tenofovir. Interferon therapy is considered successful if the patient achieves a sustained virological response (HBV DNA < 2000 IU/ml and normal ALT) 24 weeks after treatment which occurs in fewer than 30%. High rates of relapse and the side effect profile of interferon make this an unpopular option and no more than 12% of patients may clear infection (HBsAg loss) over 5 years (4,5). The majority of patients and clinicians therefore opt for treatment with nucleos(t)ide analogues which suppress viral replication resulting in resolution of fibrosis, reversal of cirrhosis and reduction in the incidence of hepatocellular carcinoma (HCC). Side effects of treatment are rare although renal tubular toxicity is described with Tenofovir. Viral resistance to Tenofovir is not reported but low rates of resistance have been described with Entecavir. However, nucleoside analogues rarely result in HBsAg loss and treatment must be maintained and monitored (HBV viral load, LFTs and ultrasounds) everv 6 months indefinitely leading to massive health care costs - the drugs alone cost £3500 per patient per year with monitoring costs and patient productivity losses increasing the burden (6).

Two recent papers have addressed the issue of finite therapy in patients with HBeAg negative chronic HBV infection (7,8). The original paper by Hadziyiannis and colleagues assessed nucleos(t)ide withdrawal after a minimum of four years' treatment in a group of patients infected with HBV genotype D. These patients were allowed to undergo a virological flare and were followed up for 6 years. Eventually, 30% lost HBsAg. In contrast, Seto assessed the impact of nucleos(t)ide withdrawal in 184 patients infected with HBV genotypes B or C after two years of treatment. Hepatitic flares or resumption of high level viral replication was not permitted so the majority of patients returned to drug treatment. Interim analysis of a similar study presented by Berg et al at EASL 2015 confirmed the findings of Hadziyiannis up to one year after nucleos(t)ide cessation.

High level viral replication is associated with suppression of HBV-specific adaptive immune responses leading to viral persistence (9). Recent data suggest that there is partial restoration of immune responses in patients on long term treatment with antiviral drugs that suppress viral replication (10).

Interferon (standard or pegylated) has been used in the treatment of HBV for 20 years due to its antiviral and immunostimulatory effects. Combining interferon with nucleos(t)ide analogues as initial treatment for HBV infection does not improve therapeutic efficacy (4). However, a number of authorities now believe that sequential therapy (with or without a short break) may amplify immune responses due to the complementary immunological effects of IFN and nucleos(t)ide analogues on innate and adaptive arms respectively and result in increased rates of HBsAg clearance. Based on

NUC-B PROTOCOL Version 2.0 12 th Aug 2016	Sponsor Imperial College
--	-----------------------------

the above, we argue that it is timely to evaluate management options which may result in a cure of HBV, release patients from indefinite drug treatment and increase cost effective care.

1.1 CLINICAL SETTING

The trial will be conducted in an outpatient setting in specialist Hepatology or Infectious Diseases clinics treating chronic viral hepatitis patients. The patient population to be addressed have chronic hepatitis B virus infection in the HBeAg negative hepatitis phase of the disease. The patients will already be on treatment with nucleoside or nucleotide analogues for viral suppression. In routine standard of care this group of patients would remain on treatment indefinitely with reviews in clinic every 3 - 6 months.

1.2 Comparison of treatment strategies

The trial will compare the efficacy of two treatment strategies to achieve loss of HBsAg

A. Control Arm

Patients randomised to the Treatment Withdrawal arm will discontinue their nucleoside analogue treatment at baseline.

B. Interferon Arm

Patients randomised to switch from nucleoside analogues to Pegylated interferon will discontinue their current therapy at baseline. No treatment will be given for 4 weeks and then they will commence pegylated interferon 180 mcg s.c. o.w $\alpha 2a$. and will continue taking weekly interferon for a total of 16 weeks. They will subsequently discontinue all antiviral medications.

1.2.1 Immunology studies

Elimination of HBV is dependent on robust innate (NK cell) and adaptive (CD4 / CD8 T cells) immune responses which are defective in chronic infection (9). It is postulated that HBsAg loss is most likely where the number of infected hepatocytes is low and the cellular immune response is amplified by the management strategy.

Suppression of viral replication has been shown to partially restore HBV-specific T cell responses. By contrast NK cells but not T cell responses are amplified by interferon therapy (11). The purpose of the mechanistic studies is therefore to determine whether sequential therapy can harness both arms of the immune response to optimise cure rates. Peripheral blood mononuclear cells will be isolated at several timepoints during the study and stored in liquid nitrogen. Enumeration of interferon gamma producing T cells will be performed using ELISPOT assays after incubation of peripheral blood mononuclear cells for 48 hours with HBV peptides. NK cell phenotype and function will be analysed using multiparameter flow cytometry to quantify activating and inhibitory receptors, intracellular cytokine production and degranulation.

In a subset of ~20 consenting patients liver biopsy or fine needle liver aspirates will be obtained to allow quantification of the intrahepatic & cccDNA and to characterise intrahepatic T and NK cells using FACS Dynamic changes in the serum HBsAg concentration will be correlated with peripheral blood cellular immune responses and with cccDNA levels.

1.2.2 Virology studies

HBsAg loss is associated with clearance of HBV-infected hepatocytes and elimination of cccDNA. Earlier studies suggest that the change in HBsAg concentrations in serum reflect the changes in cccDNA concentration in hepatocytes and therefore may represent an ideal biomarker for identifying patients who are moving towards HBsAg loss.

Samples will be taken at various timepoints to track the dynamics of HBsAg concentration changes and to enable an analysis of the predictive value of this biomarker. HBsAg concentrations will be performed using the Abbott Architect qHBsAg system in [name] laboratory.

		Sponsor
NUC-B	PROTOCOL Version 2.0 12 th Aug 2016	Imperial College

There are 7 different genotypes and a number of variants in the pre-C/C and S open reading frames of the hepatitis B virus. Viral genotypes have been associated with variation in the natural history of infection and with the response to treatment. At baseline all patients will have undetectable virus in their serum but samples taken 4 weeks after withdrawal should have sufficient circulating virus to allow genotype and sequencing of the virus. Genotyping with be performed in [name] laboratory.

In patients undergoing liver biopsy prior to baseline a sample will be used to measure the cccDNA level quantitatively using an in-house real-time PCR assay in [name] laboratory

1.3 Rationale for the study

There are estimated to be 300,000 patients with chronic HBV infection in the UK and 250 million worldwide (1, 2). Approximately 10% of these individuals require treatment which therefore imposes a significant treatment cost which is perpetuated due to the need for constant viral suppression to derive clinical benefit. Nucleos(t)ide analogue therapy is effective in suppressing the virus and we know that successful suppression reduces the risk of progression to decompensation or from hepatitis to cirrhosis. However, the risk of liver cancer is not completely eliminated. Frequent and careful monitoring is required to ensure the success of nucleos(t)ide analogues which depends on patient adherence, avoidance of viral resistance and a low rate of adverse events. Treatment therefore imposes a burden of medical monitoring visits and expensive virological assays. Finite therapy which results in viral elimination (HBsAg loss) would be more convenient to the patients and financially benefit the health service. Furthermore the risk of liver cancer amongst patients who have lost HBsAg is substantially reduced.

1.4 Risk / Benefit Assessment

Three papers have addressed the issue of finite therapy in patients with HBeAg negative chronic HBV infection over the last three years. The first looked at nucleos(t)ide withdrawal after a minimum of 4 years treatment in a group of patients infected with HBV genotype D(7). These patients were allowed to undergo a virological flare and were followed up for 6 years. Eventually 30% lost HBsAg. In contrast Seto looked at the impact of nucleos(t)ide withdrawal in 184 patients after two years of treatment(8). Significant differences in trial design affected the outcome: hepatitic flares or resumption of high level viral replication was not permitted so the majority of cases were returned to drug treatment.

High level viral replication is associated with suppression of HBV-specific adaptive immune responses leading to viral persistence (9). Recent studies suggest that there is partial restoration of T cell responses during long term treatment with nucleos(t)ide analogues (10). Interferon therapy appears to amplify NK cell but not T cell responses whilst treatment withdrawal also amplifies innate immune responses (11, 12). Interferon treatment after a short period of nucleos(t)ide withdrawal should therefore maximise immune responses and allow clearance of infected hepatocytes leading to HBsAg loss.

Interferon (standard or pegylated) has been used in the treatment of HBV for 20 years due to its antiviral and immunostimulatory effects (4, 13). Combining interferon with nucleos(t)ide analogues as initial treatment for HBV infection does not improve off-treatment virological control(4). However, adding pegylated interferon after a prolonged course of nucleos(t)ide analogue treatment increases therapeutic efficacy in HBeAg positive patients (14). It is now an ideal time to evaluate management options which result in a cure for HBV and release patients from indefinite drug treatment and the associated NHS cost.

2 OBJECTIVES AND ENDPOINTS

The aim of this trial is to explore whether finite treatment with nucleos(t)ide analogues is feasible in patients with HBeAg negative chronic HBV infection. This aim encompasses an exploration of therapeutic strategies to achieve HBsAg loss; specifically the trial is designed to evaluate whether

		Sponsor
NUC-B	PROTOCOL Version 2.0 12 th Aug 2016	Imperial College

a short course of pegylated interferon after nucleos(t)ide analogue withdrawal stimulates antiviral immunity sufficiently to increase the rate of HBsAg loss.

2.1 Primary Objective

The primary objective is to determine the rate of HBsAg loss three years after randomisation in patients with HBeAg-negative chronic HBV infection. The rate of HBsAg loss will be compared in patients with simple treatment discontinuation against patients who are given a short course of pegylated interferon after nucleos(t)ide withdrawal.

Loss of HBsAg, the most important serological marker of HBV infection, is widely accepted (including by FDA & EMA) as an indication of cure in chronic HBV infection and is associated with absence of long term sequelae in non-cirrhotic patients. HBsAg is a cheap and universally available serum marker. Loss of HBsAg allows patients to be discharged from follow-up with consequent health-economic benefits.

2.2 Secondary Objectives

- 1. To explore the safety of nucleoside withdrawal
- 2. To explore whether using interferon therapy in conjunction with treatment cessation is safe
- 3. To compare the number of patients in each treatment arm who become inactive HBV carriers.
- 4. Identification of virological and immunological biomarkers which predict a group of patients in which the loss of HBsAg is feasible
- 5. Correlate changes in HBsAg quantification and/or HBsAg status with innate and adaptive immune responses to HBV
- 6. To identify changes in immunological responses to HBV which occur after treatment withdrawal and after sequential NUC/IFN treatment

2.3 Primary Endpoint

The primary endpoint will be the proportion of patients who lose HBsAg in each treatment arm 3 years after randomisation. Qualitative assays of HBsAg will be conducted on patients every 6 months using standard laboratory ELISA assays. Loss of HBsAg will be confirmed by repeating the test at least one month after the initial negative result. Patients in whom both tests are negative will be deemed to have lost HBsAg.

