5.3 Visit Schedules Control Arm

Control A	,,,,											1	1
Visit number	1	2	3	4	5	6	7	8	9	10	11	12	13
Week	-4	0	4	8	12	16	24	32	52	78	104	130	156
Control Group	Screening ²	Baseline	Post week 4	Post week 8	Post week 12	Post week 16	Post week 24	Post month 8	Post month 12	Post Month 18	Post month 24	Post month 30	Post month 36
Consent	Х												
Demographic data	х												
Inclusion / Exclusion		Х											
Randomisation		Х											
Medical history	Х												
Vital signs	х	Х	Х	Х	Х	х	Х	х	Х	Х	Х	х	Х
Physical examination	х								Х		Х		х
Liver biopsy ¹	х												
USS/Fibroscan	х												
HBV Genotyping			Х										
qHBsAg	х												
HBsAg		Х	Х				Х		Х		Х		Х
HBV DNA	х	Х	Х	Х	Х	Х	Х	Х	Х	Х	Х	х	Х
LFTs	Х	Х	Х	Х	Х	Х	Х	Х	Х	Х	Х	х	х
Thyroid function	х												
Electrolytes & creatinine	х												
Prothrombin time	х	Х	Х	Х	Х	Х	Х	Х	Х	Х	Х	Х	Х
FBC	Х		Х				Х	Х	Х	Х	Х	х	х
PBMC collection (for immunology assays)		Х	Х				Х		Х		Х		х
Plasma/serum storage (for virology)		Х	х				Х		Х		Х		х
Adverse events		Х	Х	Х	Х	х	Х	Х	Х	Х	Х	х	х
Concomitant medications	х	Х	Х	Х	х	х	Х	х	Х	Х	Х	х	Х
Pregnancy test		Х											

Liver biopsy to be performed between screening and baseline in a sub-set of ~20 patients, 2. Baseline to occurs 4 – 12 weeks after initial screening

PROTOCOL Version 2.0 12th Aug 2016

Sponsor Imperial College

Interferon arm

Visit number	1	2	3	4	5	6	7	8	9	10	11	12	13	14	15	16
Week	-4	0	4	6	8	12	16	20	24	32	42	52	78	104	130	156
Interferon Group	Screening ²	Baseline	Gap week 4	IFN week 2	IFN week 4	IFN week 8	IFN week 12	IFN week 16	Post IFN week 4	Post IFN week 12	Post IFN week 22	Post randomisation month 12	Post randomisation Month 18	Post randomisation month 24	Post randomisation month 30	Post randomisation month 36
Consent	х															
Demographic data	х															
Inclusion / Exclusion		х														
Randomisation		х														
Medical history	х															
Vital signs	х	х	х	х	х	х	х	х	х	х	х	Х	Х	Х	Х	Х
Physical examination	х											Х		Х		Х
Liver biopsy ¹	х															
Ultrasound/Fibroscan	Х															
HBV Genotyping			х													
qHBsAg	х															
HBsAg		х	Х						х			Х		Х		Х
HBV DNA	х	х	х	х	х	х	х	х	х	х	х	Х	Х	Х	Х	Х
LFTs	х	х	х	х	х	х	х	х	х	х	х	х	Х	Х	Х	Х
Thyroid function	х				х			х		х						
Electrolytes & creatinine	Х		Х			Х		Х		Х		Х				
Prothrombin time	х	х	х	х	х	х	х	х	х	х	х	Х	Х	Х	Х	Х
FBC	х		Х	Х	Х	Х	Х	Х	Х		Х	х		Х		Х
PBMC collection (for immunology assays)		Х	х					Х	Х			х		Х		Х

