8 STATISTICAL ANALYSES

8.1 Sample Size and power considerations

HBsAg loss is the primary endpoint; the trial will compare the rate of HBsAg loss in patients three years after cessation of nucleos(t)ide analogues with the rate of HBsAg loss in patients treated with pegylated interferon after cessation of nucleos(t)ide analogues. Only one published study provides an estimate of the rate of HBsAg loss in patients who stopped treatment after 4 years of nucleos(t)ide analogues which was 10% at 1 year,18% at 2 years and 24% at 3 years. A similar study reported by Berg (EASL 2015) confirmed the 10% HBsAg loss reported at 1 year. In the present study we will recruit some patients who have had treatment with nucleos(t)ide analogues for only 3 years and we will therefore use a conservative assumption for the rate of HBsAg loss in this group at 15% at 2 years and 20% at 3 years.

There is no data on the rate of HBsAg loss in patients who have been treated with nucleos(t)ide analogues and subsequently been treated with pegylated interferon. In a trial of pegylated interferon for naïve HBeAg negative hepatitis infection 42.4% had lost HBsAg at the end of follow up if the level of HBV DNA had been <70 IU/ml at the end of treatment. As this is an exploratory study we have assumed that the rate of HBsAg loss in this group will be 30% at 2 years and 40% at 3 years. This increment would represent the very significant clinical benefit which would justify the use of interferon (with associated side effects) in this group of patients.

A trial with 90% power to detect a difference in HBsAg loss between these groups (40% vs 20%) at the P < 0.05 threshold would require 109 subjects in each arm. Therefore allowing for ~10% withdrawal / dropout in each arm we will aim to recruit 120 subjects to each arm; a total of 240 patients in total. If either arm is discontinued after the pilot, then there will still be at least 80% power in comparison with an alternative trial arm in the post pilot participants.

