9.13 End of Trial

The end of the trial will be last patient last visit.

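### The schedules omit the 6-monthly HBsAg tests promised in section 2.3 and provide no visit to confirm a first negative at week 156; power is 76% to 90%, depending on unscheduled tests

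*Protocol*

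**What the plan says.** Protocol section 2.3 sets the endpoint: "The primary endpoint will be the proportion of patients who lose HBsAg in each treatment arm 3 years after randomisation". It gives the testing frequency: "Qualitative assays of HBsAg will be conducted on patients every 6 months using standard laboratory ELISA assays". It then sets a two-test rule: "Loss of HBsAg will be confirmed by repeating the test at least one month after the initial negative result", followed by "Patients in whom both tests are negative will be deemed to have lost HBsAg".

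The schedules in section 5.3 differ from this:

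- The control and interferon tables mark HBsAg at weeks 0, 4, 24, 52, 104 and 156.
- The alternative interferon table marks weeks 0, 4, 20, 52, 104 and 156.
- Visits exist at weeks 78 and 130 in all three tables, with blood taken for HBV DNA and liver function, but neither HBsAg nor serum storage is marked there.
- The last column is week 156 (in the interferon tables, "Post randomisation month 36"). No confirmatory visit follows it, and the tolerance for late visits is 10 days either way.

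Section 5 ends follow-up 3 years after randomisation. Section 9.13 says: "The end of the trial will be last patient last visit". Section 5.3 describes additional recorded visits for safety monitoring and does not mention confirming HBsAg loss.

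**The concern.** The primary endpoint needs two negative tests at least a month apart. A first negative at week 24, 52 or 104 is followed by another scheduled HBsAg test. A first negative at week 156 is not, and 10 days of tolerance cannot supply the month.

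Because week 130 has no HBsAg test, this affects every patient who loses HBsAg between weeks 104 and 156, which is the whole third year of a 3-year endpoint. If those losses go unconfirmed, the absolute rates are understated, the planned 20-point difference shrinks and power falls.

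If sites recall patients on their own initiative, the trial is open label, so the effort to obtain a repeat could differ between arms.

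**Working it through.** **Inputs.** From section 8.1: control loss 15% at 2 years and 20% at 3 years. For the interferon arm, "we have assumed that the rate of HBsAg loss in this group will be 30% at 2 years and 40% at 3 years". Also from 8.1: 109 per arm, 90% power, P < 0.05. Sidedness is not stated; two-sided is assumed because it reproduces the sample size. Allocation is equal (section 5.2).

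**Formula.** Two proportions, pooled variance under the null, no continuity correction, with p̄ the mean of p1 and p2:

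power = Φ{ [ |p2 − p1| − 1.96 √(2p̄(1 − p̄)/n) ] / √( [p1(1 − p1) + p2(1 − p2)]/n ) }

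**Step 1: reproduce the plan.** For 20% vs 40% and n = 109: (0.200 − 1.96 × 0.0621)/0.0606 = 1.29, so power is 90.2%. Solving for 90% gives 109 per arm, as stated.

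**Step 2: share of events arising in year 3.** Control: (20 − 15)/20 = 25%. Interferon: (40 − 30)/40 = 25%. With 109 per arm, expected events are 109 × (0.20 + 0.40) = 65.4, of which 109 × (0.05 + 0.10) = 16.4 arise in year 3.

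**Step 3: no week-130 test and no week-156 first negative confirmed.** Countable rates are the 2-year rates, 15% vs 30%: (0.150 − 1.96 × 0.0566)/0.0556 = 0.70, so power is 75.9%. Restoring 90% would take 161 per arm.

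**Step 4: week-130 tests done, week-156 first negatives unconfirmed.** Assuming that year-3 losses are evenly spread, half are first negative at week 130 and confirmed at week 156. Rates are 17.5% vs 35%: (0.175 − 1.96 × 0.0596)/0.0584 = 1.00, so power is 84.0%. About 8 events (16.4/2) stay unconfirmed.

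**Step 5: all confirmed.** Rates are 20% vs 40% and power is 90.2%.

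| Year-3 losses confirmed | Rates | Power, n = 109 |
|---|---|---|
| None | 15% vs 30% | 75.9% |
| Half | 17.5% vs 35% | 84.0% |
| All | 20% vs 40% | 90.2% |

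**Step 6: uneven confirmation, as a bound.** If all week-156 first negatives were confirmed in the interferon arm and none in the control arm, the observed difference would be 40 − 15 = 25 points. The reverse gives 30 − 20 = 10 points. The planned difference is 20.

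**The case against.** A reader might infer that a first negative at week 156 can never count, that such a patient is a failure by definition, and that the trial therefore has 76% power. The documents do not support this. Section 2.3 says the repeat will be done and sets no latest date, and nothing forbids a test after week 156. Nor does the protocol say how a negative with a missing repeat is classified; the analysis plan, which is not shown, may settle that. So 76% is the bottom of a range.

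The HBsAg row may also show the samples for central quantification. Its post-baseline marks in the two main tables match the months for quantitative HBsAg in section 2.4 (1, 6, 12, 24 and 36). The 6-monthly local ELISA may simply have been left off. That is possible, but then the assay that defines the primary endpoint appears in no schedule, and sections 2.3 and 5.3 still need reconciling.

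Finally, the loss is proportional on the planning rates. The risk ratio stays at 2.0, and the odds ratio moves only from (0.40/0.60)/(0.20/0.80) = 2.67 to (0.30/0.70)/(0.15/0.85) = 2.43. This stands: if confirmation is equally incomplete in both arms, the main harm is lost power and understated absolute rates. It does not cover recall that differs by arm.

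The point cannot be deferred to an analysis plan. Such a plan can classify an unconfirmed negative but cannot produce a blood sample that was never taken.

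**Conclusion.** The point holds as a contradiction in how the primary endpoint is ascertained. Section 2.3 requires 6-monthly tests and a confirmatory repeat. The schedules, the follow-up period and the end-of-trial definition provide neither the tests at months 18 and 30 nor a visit for confirming a first negative at week 156.

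The size depends on how many off-schedule tests are obtained: 76% to 90% power with 109 per arm. This rests on the protocol's own planning rates, read as true loss by each time point, on a two-sided 5% test and, for the 84% figure, on even spread of losses over year 3. Bias between arms is a risk if recall is ad hoc, but nothing in the protocol shows that it would occur.

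**What to change.** Reconcile sections 2.3 and 5.3:

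1. Add qualitative HBsAg to the existing week 78 and week 130 visits in every arm's schedule, including the alternative interferon schedule.
2. Schedule one confirmatory HBsAg sample at least one month after week 156 for any patient first negative at that visit.
3. Align the end-of-trial definition in section 9.13 with that sample.

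The cost is a schedule amendment, one ELISA on blood drawn at each of two existing visits, one extra blood draw for about 8 to 16 patients on the planning rates (about 8 if the week-130 test is in place and losses are evenly spread), and closure about one month later.
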